5.3 Stopping rule and data monitoring

The phase IIa portion of the trial will be stopped for the lack of efficacy with one interim analysis to be conducted when the first 24 eligible patients have finished their 42 days follow up. The stopping rule is specified in Section 5.2.

CHARMS Protocol v1.0 (10.30.13)	Version 5.0 (10.6.15)
Version 2.0 (12.09.13)	Version 6.0 (08.29.16)
Version 2.1 (03.07.14)	Version 7.0 (04.26.17)
Version 3.0 (06.17.14)	Version 8.0 (05.24.17)
Version 4.0 (11.06.14)	Version 9.0 (08.10.17)

The phase IIa portion of the trial will monitor the dose-limiting toxicities (DLT), defined as acute GvHD grades III-IV within 42 days following the administration of VSTs or grades 3-5 non-hematologic adverse events that are at least possibly related to the T cell product within 28 days of the last dose that are not due to the pre-existing infection or the original malignancy or pre-existing co-morbidities as defined by the NCI Common Terminology Criteria for Adverse Events (CTCAE), Version 4.X.

*Note - Grade 3 and 4 expected reactions seen with the use of T cell-based immunotherapy, such as fever and hypotension requiring pressor support, will not be considered a DLT. Any other grade 3 or greater toxicity felt to be related to or resulting from Cytokine Release Syndrome (CRS) is included in the DLT. Grade 3 and 4 CRS infusion reactions that are persistent beyond 72 hours will be reported to the FDA in an expedited fashion, and will be considered a treatment-limiting toxicity.

The proportion of events will be monitored using a stopping guideline based on a Pocock-type boundary for repeated testing for toxicity.⁶¹ The risk of DLT is considered to be moderate in this population, assumed to be 25%. The following sequential boundaries will be used to monitor dose-limiting toxicity rate:

# pts	1-3	4	5-7	8-9	10-11	12-14	15-17	18-20
DLT<	--	4	5	6	7	8	9	10
# pts	21-22	23-25	26-28	29-31	32-34	35-37	38-40	41-43
DLT<	11	12	13	14	15	16	17	18
# pts	44-46	47-49	50					
DLT<	19	20	21					

The trial will be stopped if the cumulative number of patients with DLT is equal to or exceeds the boundary listed in the above table. This stopping rule yields the probability of crossing the boundary at most 5% when the true DLT rate is 25%, where the expected number of DLT is about 12. The probability of crossing the boundary is 62.7% is when the true DLT rate is 40%.

If a patient experiences Grade 5 toxicity that is at least possibly related to the product, we will hold all infusions on the study until both the incident in question and the infused product have undergone a thorough internal review and the outcome discussed with the FDA.

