- Safety including acute GVHD grades III-IV within 42 days of the last dose of VSTs or grades 3-5 non-hematological adverse events within 28 days of the last VST dose and that are not due to the pre-existing infection or the original malignancy or pre-existing co-morbidities as defined by the NCI Common Terminology Criteria for Adverse Events (CTCAE), Version 4.X.

Secondary Endpoints

- Antiviral responses 42 days after the first dose of VSTs
- Effects of partially HLA-matched VSTs on viral loads
- Persistence of partially HLA-matched VSTs and effects on clinical signs/symptoms
- Reconstitution of antiviral immunity at 1, 2, 3, 4,6 weeks and 3 months
- Viral reactivations within 12 months
- Secondary graft failure at 30 days
- Chronic GVHD at 3 months, 6 months and 12 months
- Clinical response to VST infusions at 6 weeks and 3 months
- Effects of HLA matching
- Effects of choosing a line with confirmed antiviral activity through one or more shared alleles
- Overall survival at 3 months, 6 months and 12 months

CHARMS Protocol v1.0 (10.30.13)	Version 5.0 (10.6.15)
Version 2.0 (12.09.13)	Version 6.0 (08.29.16)
Version 2.1 (03.07.14)	Version 7.0 (04.26.17)
Version 3.0 (06.17.14)	Version 8.0 (05.24.17)
Version 4.0 (11.06.14)	Version 9.0 (08.10.17)

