3 STUDY ENDPOINTS

3.1 Primary Endpoint

The primary objectives for this pilot study are feasibility and safety. Safety of administration of VSTs is 42 days for GVHD and 28 days for other toxicities. Except as noted below, the safety endpoint will be defined as acute GvHD grades III-IV within 42 days of the last dose of VSTs or grades 3-5 non-hematologic adverse events related to the T cell product within 28 days of the last VST dose and that are not due to the pre-existing infection or the original malignancy or pre-existing co-morbidities as defined by the NCI Common Terminology Criteria for Adverse Events (CTCAE), Version 4.X.

Grade 3 and 4 expected reactions seen with the use of T cell-based immunotherapy, such as fever and hypotension requiring pressor support, will not be considered a safety endpoint. Any other grade 3 or greater toxicity felt to be related to or resulting from Cytokine Release Syndrome (CRS) is included in the safety endpoint. Grade 3 and 4 CRS infusion reactions that are persistent beyond 72 hours will be reported to the FDA in an expedited fashion, and will be considered a treatment-limiting toxicity.

Toxicities to consider include GI toxicity, renal toxicity, hemorrhagic toxicity, cardiovascular toxicity (hypotension, cardiac arrhythmia and left ventricular systolic dysfunction), neurological toxicity (somnolence and seizure), coagulation toxicity, vascular toxicity and pulmonary toxicity.

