4.3 Modified Follow-Up & Off Study Criteria

4.3.1 Criteria for Modified Follow-Up

The following criteria will result in the patient being ineligible for further treatment on the protocol, although response data will continue to be collected as applicable:

- 4.3.1.1 Any patient who develops irreversible, life threatening, Grade 3-4 acute GvHD within 42 days, Grades 3-5 non-hematologic adverse event within 28 days from last VST dose and considered to be primarily related to VST injection. In such patients, the toxicities will be followed until resolution or until their off study date.
- 4.3.1.2 Any patient who receives any other hematopoietic cell product. In such patients, adverse event data collection will cease.
- 4.3.1.3 Any patient who receives therapy for relapse of their primary malignancy. In such patients adverse event data collection will cease.
- 4.3.1.4 Any patient who experiences Grade 3 or 4 cytokine release syndrome that persists beyond 72 hours. In such patients, the toxicity will be followed until resolution or until their off study date.

Patients who meet “modified follow-up” criteria remain on long-term follow-up as per the required assessments table 4.2.2.

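### The primary safety endpoint has two attribution rules, neither matching the monitored DLT, and the DLT's dose anchor leaves the stopping count open for re-dosed patients

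*Combined protocol and SAP*

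**What the plan says.** Three places define the safety event. All three exclude adverse events caused by the infection, the malignancy or earlier co-morbidity. They differ in attribution and in the dose from which time runs.

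- **Study Schema, primary endpoints.** GVHD limb: "acute GVHD grades III-IV within 42 days of the last dose of VSTs". Adverse-event limb: "grades 3-5 non-hematological adverse events within 28 days of the last VST dose and that are not due to the pre-existing infection". No relation to the product is required.
- **Section 3.1.** GVHD limb: "acute GvHD grades III-IV within 42 days of the last dose of VSTs". Adverse-event limb: "grades 3-5 non-hematologic adverse events related to the T cell product within 28 days of the last VST dose".
- **Section 5.3 (DLT).** GVHD limb: "within 42 days following the administration of VSTs". Adverse-event limb: "at least possibly related to the T cell product within 28 days of the last dose".

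Section 5.3 compares the cumulative number of patients with a DLT against a Pocock-type boundary over the 50 patients of the phase IIa portion. It stops the trial when the count reaches the boundary. It states a crossing probability of at most 5% at a 25% DLT rate, with about 12 expected DLTs, and 62.7% at a 40% rate.

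Section 2.4.2.5 allows up to four further infusions, the first at day 28 and the rest at least two weeks apart. Section 4.2.1 restarts the follow-up schedule at each infusion. No section says whether an event after an earlier infusion still counts once another is given.

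**The concern.** Two separate problems follow.

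**Reporting.** Safety is a primary objective. Under the Schema, a grade 3 event that is unrelated to the product but not covered by an exclusion counts. Under section 3.1 it does not. An event judged only possibly related counts under section 5.3, and whether it meets section 3.1 depends on how strictly an assessor reads related. The same patients can give different primary safety rates, and either may differ from the rate that was monitored.

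**Stopping.** Take a possibly related grade 3 event on day 10 in a patient infused again on day 28. If the last dose means the final dose received, day 10 precedes the window and the patient is not a DLT for that event. If it means the most recent dose at the time, the patient is. The GVHD limb in section 5.3 names no dose, so it can be read from the first, the last or any infusion. A rule meant to stop the trial for toxicity should not depend on which reading the data manager adopts. The literal reading errs towards undercounting.

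**Working it through.** **Step 1. Reproduce the boundary.** Inputs are the table in section 5.3, 50 patients, and stopping when the count equals or exceeds the boundary. Let d(n,k) be the probability of k DLTs after n patients without having stopped:

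d(n,k) = d(n−1,k)·(1−p) + d(n−1,k−1)·p

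After each patient from n = 4, the mass at or above the boundary is removed and added to the crossing probability.

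| True rate p | Computed crossing | Stated |
|---|---|---|
| 25% | 5.04% | at most 5% |
| 40% | 62.8% | 62.7% |

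At 25% the expected number of patients treated is 48.43, so expected DLTs are 48.43 × 0.25 = 12.1 (stated: about 12). The excess of 5.04% over 5% is rounding. Stopping only when the boundary is exceeded would give 1.6% and 48.2%, so the stated figures match the text's equal-or-exceeds rule. The boundary is sound. What is open is which events enter it.

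**Step 2. Windows under each reading.** The earliest five-dose calendar is day 0, day 28, then 28 + 14 = 42, 56 and 70.

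| Reading | Adverse-event window | GVHD window |
|---|---|---|
| Final dose only | days 70 to 98 | days 70 to 112 |
| First dose only (possible for section 5.3 GVHD) | not applicable | days 0 to 42 |
| Any dose, or most recent dose | days 0 to 98 | days 0 to 112 |

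Under the final-dose reading, 70/98 = 71% of adverse-event time and 70/112 = 63% of GVHD time fall outside the window. With two doses (days 0 and 28), the windows are days 28 to 56 and 28 to 70, so 28/56 = 50% and 28/70 = 40% fall outside. With one dose all readings agree.

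**Step 3. Can a DLT precede a later dose?** Three provisions limit this.

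- Section 2.4.2.5 refers to significant toxicity from the initial infusion. Significant is undefined. The condition can be read as attached only to its second route (incomplete response) and not to its first (patients given drugs such as steroids, which section 2.5.5 calls standard GVHD therapy).
- Section 2.3.2 excludes active acute GVHD of grades II-IV. A resolved episode is not active.
- Section 4.3.1.1 ends treatment for events "considered to be primarily related to VST injection", and its GVHD limb is qualified as irreversible and life threatening. Both conditions are narrower than the DLT.

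A resolved grade III GVHD, or a possibly related grade 3 event, can therefore come before a later infusion. The route is narrowed but not closed.

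**Step 4. Effect of undercounting.** Let m be the share of DLT patients not counted. The counted rate is 0.40 × (1 − m), put through the Step 1 recursion. The documents give no value for m, so the range is assumed. It cannot exceed the share of DLT patients who are infused again.

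| m | Counted rate | Crossing |
|---|---|---|
| 0 | 40% | 62.8% |
| 5% | 38% | 52.5% |
| 10% | 36% | 42.0% |
| 20% | 32% | 23.2% |

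**The case against.** The best defence is that the last dose means the most recent dose. Section 4.3.1.1 uses similar wording to decide whether a patient may be treated again, where no other meaning is possible, and section 4.2.1 restarts follow-up at each infusion. The day-10 event would then enter a cumulative count, and nothing says that it leaves. On the minimum-spacing calendar this reading has no gaps. It is reasonable and may be what was intended, but section 5.3 does not state it and its GVHD limb names no dose at all.

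It is also fair that redosing after toxicity is restricted, that safety is summarised descriptively with no test resting on it (section 5.4), and that five doses at minimum spacing is the extreme case. The documents do not give the share of patients infused more than once. If the true DLT rate is low, the readings hardly differ for stopping: crossing is 0.2% at 15% and 1.2% at 20% with every event counted.

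Three stronger readings are tempting and are not supported.

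- A reader might infer that the differing attribution rules leave the stopping count undetermined. They do not. Only the section 5.3 DLT meets the boundary, and it has one attribution rule.
- A reader might infer two GVHD windows of different length. Both are 42 days; only the starting dose differs.
- A reader might argue that looser attribution adds 5 or 10 points to the 25% rate, raising crossing to 16.0% or 36.9%. Those figures are the correct crossing probabilities at 30% and 35%. However, the 25% in section 5.3 already describes a DLT that includes possibly related events, and nothing in the documents supports the added points.

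**Conclusion.** The concern holds in a limited form. The adverse-event limb of the primary safety endpoint is defined in two incompatible ways, and neither matches the monitored DLT. The reported safety rate is therefore not fixed and may differ from the monitored one. This follows from the text alone.

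The stopping count is open only through the dose anchor, and only for patients given more than one infusion. The loss of crossing probability, from 62.8% to between 52.5% and 23.2% at a true 40% rate, is a sensitivity calculation. It assumes the final-dose reading and that 5% to 20% of DLT patients have no counted event. The documents do not supply that share, and the redosing restrictions and the most-recent-dose reading both argue for a smaller one. The boundary needs no recalculation. Because the inconsistency sits in a primary endpoint and a toxicity stopping rule, and is cheap to remove, it should be settled.

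**What to change.** Use one safety-event definition in the Study Schema, section 3.1 and section 5.3, with one attribution wording. The section 5.3 wording is the natural choice because it already accompanies the boundary. State that:

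- a patient counts if acute GVHD of grade III-IV occurs within 42 days after any VST infusion, or a qualifying grade 3-5 non-hematologic event occurs within 28 days after any VST infusion, with the existing exclusions kept; and
- a later infusion does not remove an event already counted.

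Anchoring to any infusion is better than one continuous period from the first infusion to 28 or 42 days after the last. Section 2.4.2.5 sets no maximum interval between doses, so a continuous period could include time beyond the scheduled assessments. The per-infusion windows use assessments that sections 4.2.1 and 4.2.2 already schedule after each dose. The collection period in section 6.2.1 is also written from the last dose and should be aligned.

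The cost is wording in three places plus that alignment. The boundary stays as it is. The one downside is that the reported safety rate may be slightly less favourable.

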5.4 Data Analysis

Safety and toxicity outcomes including adverse events, GvHD, clinical signs of viral infections, secondary graft failure and laboratory measurements will be summarized using descriptive statistics (frequency table, means, standard deviations, medians and ranges). Toxicity information including the type, severity, time of onset, time of resolution, and the probable association with the study regimen will be tabulated and summarized.

Response rate including complete response, partial response and mixed response will be summarized as frequency table. The response rate with 95% CI will be reported. Reconstitution of antiviral immunity using multimer analysis and ELISpot assays will also be summarized using descriptive statistics at each time point. Pairwise comparisons will be performed to compare changes of these immunological parameters from VST infusion to each time point of post-infusion measurements using paired t-tests or Wilcoxon signed-ranks tests. The normality assumption will

CHARMS Protocol v1.0 (10.30.13)	Version 5.0 (10.6.15)
Version 2.0 (12.09.13)	Version 6.0 (08.29.16)
Version 2.1 (03.07.14)	Version 7.0 (04.26.17)
Version 3.0 (06.17.14)	Version 8.0 (05.24.17)
Version 4.0 (11.06.14)	Version 9.0 (08.10.17)

be assessed and transformations to achieve approximate normality will be carried out if necessary. Overall survival post VST infusion will be analyzed by the Kaplan-Meier method.

Viral load reduction will be compared between the low and high HLA using the two-sample t-test. Additionally, Viral load levels will be correlated with immunological parameters using correlation coefficients. Longitudinal analysis is employed to model repeatedly-measured immunologic parameters. This will allow us to model patterns of immune response per patient while allowing for varying intercepts and slopes for a patient. Viral load levels will be correlated with immunological parameters using correlation coefficients. These modeling strategies will be considered exploratory in nature due to the limited patient numbers in this initial trial.

Overall survival since allogeneic hematopoietic stem cell transplant will be analyzed using the Kaplan-Meier method. Cumulative incidences to the time of complete/partial resolution of viral infection and viral load reduction, considering death a competing event, will be analyzed in univariate and multivariate model using the Fine and Gray method.

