3.1.7 Chronic GVHD

Chronic GVHD will be assessed 3, 6 and 12 months post VST infusion.

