4.2.2 Assessments

All assessments are considered standard-of-care unless identified below by “*.”

Pre-Infusion

1. History and physical exam including height and weight
2. Viral loads for EBV, adenovirus, CMV, HHV6, JC virus and BK virus
3. Complete acute GVHD staging and grading information including assessments of rash, diarrhea, nausea/vomiting, weight and liver function tests
4. CBC with differential, platelet count
5. Basic chemistry
6. Liver function tests (bilirubin, alkaline phosphatase, AST, ALT)
7. Tacrolimus/cyclosporine level if on these agents
8. Pregnancy test* if female patient of childbearing potential and has received a reduced intensity transplant regimen
9. Samples for research laboratory studies*

Post-Infusion

1. Viral load for the treated virus or viruses will be collected weekly at 1, 2, 3, 4 and 6 weeks, and 3 months post-infusion. Thereafter, viral load results will be followed until 12 months post infusion as clinically indicated. Additional time points may be analyzed as clinically indicated. If the treatment team is also measuring viral loads for other viruses we will follow these results.
2. Complete acute GVHD staging and grading information including assessments of rash, diarrhea, nausea/vomiting, weight and liver function tests weekly until Day 42

CHARMS Protocol v1.0 (10.30.13)	Version 5.0 (10.6.15)
Version 2.0 (12.09.13)	Version 6.0 (08.29.16)
Version 2.1 (03.07.14)	Version 7.0 (04.26.17)
Version 3.0 (06.17.14)	Version 8.0 (05.24.17)
Version 4.0 (11.06.14)	Version 9.0 (08.10.17)

3. Chronic GVHD evaluation (if present) at 3, 6, and 12 months
4. Liver function tests (bilirubin, alkaline phosphatase, AST, ALT) at 1, 2, 3, 4, 5 and 6 and 3 months.
5. Infusion-related toxicities within 24 hours and toxicity evaluation weekly until Day 30, and acute GVHD until Day 42.
6. Steroid dose weekly until Day 42, and at 3 and 6 months
7. Samples for laboratory studies at 1, 2, 3, 4, and, 6 weeks and 3 months: 30-40mls or 6-8 teaspoons will be collected at each time point. For recipients who weigh less than 10kg the amount will be reduced to 3mls/kg. Depending on clinical and laboratory viral responses samples may be collected at additional time points.*

Research laboratory studies will include:

Assessment of virus-specific immunity as measured by serum profiling, ELIspot, intracellular cytokine staining, multimer assays and/or other assays as they become available.

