Appendix I

CHRONIC GVHD ASSESSMENT

Patient's Name: _____

Date of Chronic GVHD Evaluation: _____

Time point of Evaluation (post cell infusion): Day 90 Day 180 Day 365

If the patient does not have symptoms of Chronic GVHD (cGVHD), please mark "None" below and sign and date this page. The assessment table on the attached page does not need to be completed if the patient does not have cGVHD. If the patient does have symptoms of cGVHD, please record the grade and severity below, sign and date this page and complete the assessment table on the attached page.

Maximum Grade of Chronic GvHD: **NONE**

(since the last assessment)

LIMITED localized skin involvement and/or hepatic dysfunction due to cGVHD

EXTENSIVE one or more of the following:

- generalized skin involvement; or
- liver histology showing chronic aggressive hepatitis, bridging necrosis or cirrhosis; or
- involvement of eye: Schirmer's test with < 5 mm wetting; or
- involvement of minor salivary glands or oral mucosa demonstrated on labial biopsy; or
- involvement of any other target organ

Overall Severity of Chronic GVHD: **NONE**

(since the last assessment)

MILD signs /symptoms do not interfere substantially with function and do not progress once appropriately treated with local therapy or standard systemic therapy (corticosteroids and/or cyclosporine or FK506)

MODERATE signs/symptoms interfere somewhat with function despite appropriate therapy or are progressive through first line systemic therapy (corticosteroids and/or cyclosporine or FK506)

SEVERE signs/symptoms limit function substantially despite appropriate therapy or are progressive through second line therapy

The following section is to be completed ONLY at the time of the INITIAL ONSET of Chronic GVHD:

Date of Initial Onset of Chronic GVHD: _____

- Progressive (aGVHD progressed directly to cGVHD)
- Interrupted (aGVHD resolved, then cGVHD developed)
- De novo (aGVHD never developed)
- Chronic GVHD flare (symptoms reactivated within 30 days of drug tapering or discontinuation)

The following section is to be completed IF patient has aGVHD symptoms post Day 100:

Did Acute Graft vs. Host Disease (aGVHD) develop or persist (or a flare-up that was more severe) since the date of the last assessment? **YES** **NO**

Additional Information/Comments: _____

Printed Physician Name

Physician Signature/Date

CHARMS Protocol v1.0 (10.30.13)
 Version 2.0 (12.09.13)
 Version 2.1 (03.07.14)
 Version 3.0 (06.17.14)
 Version 4.0 (11.06.14)

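### Section 5.4 states no denominator and no handling of death or loss to follow-up for chronic GVHD at 3, 6 and 12 months; a cumulative incidence would supply both

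*Combined protocol and SAP*

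**What the plan says.** The Study Schema lists among the secondary endpoints "Chronic GVHD at 3 months, 6 months and 12 months". Section 3.1.7 adds only the timing: "Chronic GVHD will be assessed 3, 6 and 12 months post VST infusion". Section 4.2.2 schedules "Chronic GVHD evaluation (if present) at 3, 6, and 12 months".

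Section 5.4 has no analysis specific to chronic GVHD. It comes under the safety outcomes, where acute and chronic disease are not separated: "Safety and toxicity outcomes including adverse events, GvHD, clinical signs of viral infections, secondary graft failure and laboratory measurements will be summarized using descriptive" and then "statistics (frequency table, means, standard deviations, medians and ranges". The next sentence reads: "Toxicity information including the type, severity, time of onset, time of resolution, and the probable association with the study regimen will be tabulated and summarized". Neither sentence gives a denominator or a rule for death or loss to follow-up.

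Two other places bear on the point. The Appendix I form has a field for "Date of Initial Onset of Chronic GVHD" and asks for maximum grade and severity "since the last assessment". The last paragraph of Section 5.4 applies the Fine and Gray method, with death as the competing event, to viral resolution and viral load reduction, but not to GVHD.

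**The concern.** Chronic GVHD develops over months in patients who may die or leave follow-up before day 365. A proportion reported at 12 months means nothing definite until one knows who is in the denominator and where the deaths went. Dividing by patients assessed at the visit and dividing by all patients infused answer different questions. With the first choice, the three time points also have three different denominators.

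GVHD deserves this care here. The synopsis promises close monitoring for any association between infusion and GVHD, and Section 1.11.2 explains that alloreactivity testing will not be a release criterion. The reported chronic GVHD figures are therefore part of the safety evidence for a partially matched product.

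The time origin is also open. Section 4.2.1 restarts the visit clock at each dose, and Section 2.4.2.5 allows up to four additional doses, from day 28 and at least two weeks apart. A patient given all five doses as early as possible has the last one on day 28 + 3 × 14 = 70, so that patient's 3-month visit falls on day 70 + 90 = 160 after first infusion.

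**Working it through.** The documents give no chronic GVHD rate, no mortality rate and no sample size for this endpoint, so there is no planned figure to reproduce. What follows is an illustration on assumed inputs.

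**Inputs**
- From the documents: at most 80 infused patients (synopsis); visits at days 90, 180 and 365 (Section 4.2.1); a 10% loss to follow-up used for sizing (Section 5.2). Applying that 10% over 12 months is my assumption.
- Assumed: net 12-month chronic GVHD risk 20%; 12-month mortality without chronic GVHD 30%; death hazard after onset k times that before, with k = 1, 2 or 4; constant hazards.

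**Hazards per year**
- Onset: λ = −ln(0.80) = 0.2231
- Death before onset: μ = −ln(0.70) = 0.3567
- Death after onset: ν = kμ

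**Cumulative incidence at 12 months, death as competing event**

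C = λ/(λ+μ) × (1 − e^−(λ+μ)) = 0.2231/0.5798 × (1 − 0.56) = 0.169

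This does not depend on k, because deaths after onset do not undo an onset. Of 80 patients, 13.5 are expected to have an onset.

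**Proportion among those alive at 12 months**

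- Alive without chronic GVHD: H = e^−(λ+μ) = 0.56
- Alive with onset: I = λ e^−ν × (1 − e^−d)/d, where d = λ + μ − ν
- Survivor proportion: I/(H + I)

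| k | I | H + I | I/(H + I) | C |
|---|---|---|---|---|
| 1 | 0.140 | 0.700 | 20.0% | 16.9% |
| 2 | 0.117 | 0.677 | 17.3% | 16.9% |
| 4 | 0.084 | 0.644 | 13.1% | 16.9% |

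The survivor figure is too high at k = 1, nearly right at k = 2 and too low at k = 4. Solving I/(H + I) = C numerically puts the crossing at about k = 2.1.

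With mortality varied over 10–50%, net risk over 10–30% and k at 1 or 2, the survivor figure exceeds C by 0 to 8 percentage points. The largest gap is 30.0% against 22.1%, at 50% mortality, 30% net risk and k = 1.

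**Proportion among all infused, lost patients counted as event-free**

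Loss hazard g = −ln(0.90) = 0.1054. The recorded proportion is

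λ/(λ+μ+g) × (1 − e^−(λ+μ+g)) = 0.2231/0.6852 × (1 − 0.504) = 0.1615, about 16.2% against 16.9%.

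**Onsets missed because the patient dies before the next visit**

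For each interval between visits, multiply the probability of being alive and unaffected at its start by the probability of being alive with onset at its end, and add the three products. The result over all infused is 15.9% at k = 1 and 14.9% at k = 2. Of the 13.5 expected onsets, 80 × (0.1693 − 0.1586) = 0.9 and 80 × (0.1693 − 0.1488) = 1.6 would go unrecorded if forms were completed only at visits.

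**Scale**

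An approximate 95% half-width for 16.9% of 80 is 1.96 × √(0.169 × 0.831/80) = 8.2 points. The distortions in the main example (about 3 to 4 points) are smaller than that. The largest in the range is about equal to it.

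**The case against.** The strongest reply is that the plan never says the table is confined to survivors. A table of patients affected by 3, 6 and 12 months, over all infused, fits Section 5.4 equally well. That is correct. A reader might infer survivor-only counting from the visit schedule, but the documents leave the denominator open. The point is the missing rule, not a wrong one.

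Second, onsets between visits are not simply lost. Appendix I looks back over the interval, time of onset is to be tabulated, serious adverse events are collected for a year after last dosing (Section 6.2.2), and a death form exists (Section 6.1). This stands for survivors and for serious cases. It does not cover a non-serious onset in a patient who dies before the next form is due, because Appendix I is tied to days 90, 180 and 365.

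Third, a reader might conclude that survivor-only figures always understate the risk. The check does not support that: the sign depends on how strongly onset raises mortality, which the documents do not give.

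Fourth, one might ask for the same analysis of acute GVHD. The documents show no defect there. It is scored weekly to day 42 (Sections 2.5.2 and 4.2.2), and grades III–IV feed the toxicity stopping rule in Section 5.3.

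Finally, descriptive summary is a legitimate choice for a secondary endpoint of a single-arm pilot. That limits the importance of the point. It does not supply the denominator.

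**Conclusion.** The point holds as a gap in the plan with a clearly better method available. Section 5.4 does not say who is counted, or what happens to patients who die or are lost, for chronic GVHD at 3, 6 and 12 months. The plan collects an onset date and already uses a competing-risk method for another outcome.

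Under the assumed inputs, a figure restricted to patients assessed at 12 months could be 20.0%, 17.3% or 13.1% against a cumulative incidence of 16.9%. A figure over all infused would be about 16.2% with 10% loss. These sizes rest on assumed risk, mortality and loss and on constant hazards. They show that the choice matters by a few points in either direction, not what the trial will find.

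The documents do not support saying that the table covers only survivors, or that any bias must be downward. Importance is low: no hypothesis, sample size, error rate or stopping rule depends on this endpoint.

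**What to change.** In Section 5.4, state that:
- chronic GVHD is estimated by cumulative incidence among all infused patients, from first infusion, using the Appendix I onset date;
- death without chronic GVHD is the competing event, and other patients without onset are censored at their last assessment;
- estimates with 95% CI are given at 3, 6 and 12 months;
- patients with chronic GVHD already present at first infusion are analysed separately, since Section 2.3.2 excludes only active acute GVHD of grades II–IV;
- the frequency table is kept, with its denominator stated at each time point.

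The cost is a few sentences in Section 5.4 and two small data steps. Appendix I must also be completed from the medical record at death or off-study, so that an onset between visits is captured. Time from first infusion must be derived for re-dosed patients, because their visit schedule restarts. No new visits or tests are needed.
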